## STUDY DESIGN

### *Subjects and Recruitment*

This study will be conducted at the UAB School of Optometry (Birmingham, AL, USA). Subjects will be recruited by word of mouth during regular clinical care. Adult (>18 years) subjects will be recruited for this study. Subjects will be excluded if they have past experience or advanced knowledge of SLs, a physical or cognitive condition that may prevent them from successfully wearing SLs (e.g., stroke), or if they are currently participating in another clinical trial. Since there is limited data on this topic and since the literature lacks a method for calculating a sample size for a five-way comparison, a true sample size calculation is not possible for this project. Since this study is preliminary in nature, 25 subjects will be recruited to gain an initial understanding of how subjects prefer to apply SLs. Five additional subjects will be recruited to account for screen failures (total of 30 subjects).

### Clinical Protocol

## *Visit 1: Baseline Visit*

**1. Subject History, Eligibility, Informed Consent:** Subjects will be asked to complete an IRB-approved screening survey to verify that they are still eligible for the study. Eligible subjects will be enrolled, consented, and requested to sign a privacy document. All relevant subject history will be gathered via a questionnaire developed by the investigators that asks about the patient's past contact lens and ocular disease history. Non-eligible subjects will be dismissed at this time.

**2. Questionnaires:** All subjects will be asked to complete the Standardized Patient Evaluation of Eye Dryness (SPEED) questionnaire because it is a validated dry eye symptoms questionnaire that asks about the most common dry eye symptoms. Subjects will also be asked to complete the Contact Lens Dry Eye Questionnaire (CLDEQ)-8 because it is a validated instrument that asks about contact lens comfort and coping mechanisms. The Orthokeratology and Contact Lens Quality of Life Questionnaire (OCL-QoL) will also be administered because it assesses the patient's visual quality of life.

**3. Visual Acuity:** Uncorrected and habitually-corrected visual acuity will be measured with a high-contrast Snellen chart. If the patient is unable to read the 20/40 letters, the investigator will pinhole over the patient's unaided or presenting refractive error correction to determine the subject's visual potential.

**4. Manifest Refraction:** The investigator will determine the subject's refractive error with a phoropter, and binocular balance will be performed if best-corrected visual acuity is equal in between eyes. Visual acuity will be recorded as described above in step 3.

**5. Slit-Lamp Biomicroscopy:** The investigator will use a slit-lamp biomicroscope to document normal and/or remarkable findings of the anterior eye structures: eyelids, conjunctiva, and cornea.

**6. Topography:** Topography will be performed with the SMap3D. The device's standard procedure will be followed, and parameters from this measurement will be sent to the manufacturer to help determine the patient's first SL.

**7: Scleral Lens Fitting:** The Europa lens will be fit based upon the manufacturer's guidelines with their fitting set. A slit-lamp biomicroscope evaluation will be performed on the trial lens to estimate the central corneal clearance and overall fit after 30 minutes of settling. SL information will be provided to the manufacturer to help determine the patient's first SL.

## *Visit 2: Dispense Visit*

**1. Visual Acuity:** Visual acuity with habitual correction will be measured with a high-contrast Snellen chart. If the patient is unable to read the 20/40 letters, the investigator will pinhole over the patient's unaided or presenting refractive error correction to determine the subject's visual potential.

**2. Slit-Lamp Biomicroscopy:** The investigator will use a slit-lamp biomicroscope to document normal and/or remarkable findings of the anterior eye structures: eyelids, conjunctiva, and cornea.

**3. Lens Dispense:** The investigator will orient the patient and apply the ordered SLs to each eye. The investigator will use a slit-lamp biomicroscope and OCT to evaluate the SLs after 30 minutes of lens settling. If the lenses fit acceptably, the patient will undergo application and removal training (based on the randomization order

determined during step 4). If the lenses do not fit acceptably, new lenses will be ordered, and the subject will be scheduled for a follow up visit for after the study lenses arrive.

**4. Randomization:** The investigator will access the online randomization tool (REDCap) and determine the order by which subjects will apply their lenses (*DMV inserter with an open end (A), DMV inserter with a closed end (B), three fingers (C), o-ring (D), tea light candle (E)*). Right eyes will undergo the application protocol; however, if the patient only needs a SL for their left eye, the left eye will undergo the protocol. Hand and eye dominance will be recorded. Subjects will then be instructed via training videos created by the investigators on how to do each application method. Each training video will be shown before starting each application method, and the examiner will answer the subject's questions prior to attempting the application method. The same investigator will teach each subject. Subjects will be timed during each application; however, time recording will not be made obvious. After a subject successfully completes an application method once for the designated eye, they will be asked to do the subsequent method. If a subject is unsuccessful with a method and declines to continue that method after being encouraged, the time will be recorded, and they will be allowed to try the next method. The subject will be allowed up to 15 minutes to complete each method. If the subject is unable to complete the method within that time frame, they will be instructed to do the next method to help avoid fatigue. If a patient stops a procedure before completing an application, this event will be recorded. Patients will be encouraged to try all five methods on the same day; however, subjects will be allowed to come back on a subsequent day if they get tired. Subjects will be asked to rank the ease of application for each method from easiest to most challenging after trying each method. If a subject needs a SL for their contralateral eye, they will be taught how to apply this lens after they have completed the training for their designated eye. If a subject is able to apply the lenses, they will be asked to remove the lenses as well. Only one removal method will be used (small plunger), and the removal time will also be timed for each method (timed separately from application).

**5. SL Release:** After a subject completes the application and removal process, they will be given everything they need to wear the lenses (non-preserved saline (Adipack), application devices). They will also be given a trial bottle of Boston Simplus (contact lens care system), and they will be allowed to try their lenses for about one week. Subjects will be instructed to use their preferred application method at home.

**6. SL Adaptation Form:** Subjects will be given a take-home diary to complete during the one-week trial period. This diary will ask the subject about their experience with applying and removing their lenses, their comfort, and their perception of the SLs.

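### The order of the five methods is randomized with no stated position balance and compared with no attempt-number term, which costs precision that a balanced list and one model term would recover.

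*Combined protocol and SAP*

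**What the plan says.** Visit 2, step 4 (Randomization) describes the allocation in one sentence: "The investigator will access the online randomization tool (REDCap) and determine the order by which subjects will apply their lenses". The methods are listed as "DMV inserter with an open end (A), DMV inserter with a closed end (B), three fingers (C), o-ring (D), tea light candle (E"). No Latin square, block, set of permitted sequences or other list rule appears there or elsewhere in the document.

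Each subject works through all five methods in turn: "After a subject successfully completes an application method once for the designated eye, they will be asked to do the subsequent method". On numbers, Subjects and Recruitment says that "25 subjects will be recruited to gain an initial understanding of how subjects prefer to apply SLs", and then: "Five additional subjects will be recruited to account for screen failures (total of 30 subjects"). It gives no power basis, stating that "a true sample size calculation is not possible for this project".

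The Data Collection and Analysis section proposes means and standard deviations, ANOVA for comparing methods, and alternatives such as Kruskal-Wallis if assumptions fail. It names no term for subject, sequence or attempt number.

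**The concern.** Each subject makes five related attempts on the same eye, so results may depend on attempt number as well as on method. Practice is plausible because subjects are novices: "Subjects will be excluded if they have past experience or advanced knowledge of SLs". Fatigue is plausible too, and the protocol foresees it; after the time limit on a method, "they will be instructed to do the next method to help avoid fatigue". The two work in opposite directions, and the documents do not say which dominates.

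If some methods fall early more often than others, each method's mean time or mean ease rank carries part of the order effect. The named analysis would not remove it. With five methods and 25 subjects, exact position balance is available, since 25 = 5 × 5. What is at stake is the precision of the method comparison and the readability of the descriptive means, in a small study whose purpose is to compare the methods.

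**Working it through.** The plan states no balance, power or order-effect figure, so there is none to reproduce. The check asks what unrestricted orders would produce and what a balanced list would change.

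**Inputs from the document:** 5 methods, 25 subjects (30 recruited in all), every subject trying every method, and ANOVA with no position term.

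**Assumptions, not in the document:** orders are independent random permutations of the five methods; the outcome is continuous with independent within-subject errors; the order effect is linear, with a total shift of s within-subject SD from attempt 1 to attempt 5. The range shown is s = 0.5 to 2.

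**1. Imbalance under unrestricted orders (simulation, n = 25).**
- Some method comes first 8 or more times in about 51% of trials (expected count 5).
- The mean-position gap between the earliest- and latest-placed methods averages about 0.74 positions.
- Each method expects 25 × 0.4 = 10 attempts in positions 4–5, with SD √(25 × 0.4 × 0.6) = 2.45. On average the lowest count is 6.9 and the highest 13.2.
- The probability that one given position (for example, last) is exactly balanced is 25!/((5!)^5 × 5^25) = 0.0021. Balance in all 25 method-by-position cells did not occur in 50,000 simulated trials.

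**2. Variance of an unadjusted method difference.** Within a random permutation of 1 to 5, a position has variance 2 and two positions have covariance −0.5. Their difference therefore has variance 2 + 2 + 1 = 5. The slope per position is s/4 SD. In units of the within-subject variance:
- error part: 2/25
- order part: (s/4)² × 5/25
- ratio to the balanced case: 1 + (5s²/16)/2 = 1 + 5s²/32

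| Assumed total shift s | Variance ratio | Increase |
|---|---|---|
| 0.5 SD | 1.039 | about 4% |
| 1 SD | 1.156 | about 16% |
| 2 SD | 1.625 | about 62% |

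**3. Unrestricted orders with attempt number modelled.** Simulated mean efficiency against exact balance is 0.958. Variance is therefore 1/0.958 = 1.044 times that under balance, a loss of about 4%, or 25 × 0.042 ≈ 1 subject.

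**4. Test size at nominal 5% (subject-plus-method ANOVA, no attempt number).** With unrestricted orders, size stays near 5% at shifts of 1 and 2 SD. With a balanced list, it falls to about 2.8% at 1 SD and 0.3% at 2 SD. The order effect no longer enters the method means but still inflates the residual.

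**5. The balanced list.** For five methods the Williams set has 10 sequences, made of two 5 × 5 squares. The set used twice plus one of its squares gives 25 sequences: each method is in each position exactly 5 times, and each ordered predecessor pair occurs 4 or 6 times. The set used three times gives 30 sequences, with 6 per position and 6 per pair.

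**The case against.** The strongest reply has four parts.

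- **The text is silent, not contrary.** A reader might infer that orders are drawn with no constraint. The document does not say so; the list behind the tool could already be balanced. This stands: every imbalance figure above is conditional on unrestricted draws.
- **Random order protects the comparison.** A reader might also infer that the method comparison is biased or its test invalid. Neither follows. Each method has the same expected position, and simulated test size stays near 5%. This stands, and it limits the harm to chance imbalance and lost precision.
- **Modelling attempt number does most of the work.** With that term in the model the list is worth about one subject of 25, in a study that calls itself preliminary and has no power target. This stands for the modelled comparison. It does not cover the descriptive method means, which stay unadjusted, and the plan names no such term.
- **The order effect is assumed, and the calculation does not cover ranks.** The shift of 0.5 to 2 SD is an assumption; at 0.5 SD the loss is only about 4%. It would be wrong to say that late attempts are easier, since fatigue could offset or outweigh practice. The variance figures describe a continuous outcome such as application time, not the ease ranking, and Hypothesis 2 concerns a total over all five methods, which position imbalance between methods does not affect. All of this stands.

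**Conclusion.** The point holds as a gap in specification with a cheap improvement available. Position balance and adjustment for attempt number are both unstated. If orders are unrestricted, unequal positions are close to certain with 25 subjects. The cost is chance imbalance in the reported method means and an unadjusted variance about 4%, 16% or 62% higher for an assumed shift of 0.5, 1 or 2 within-subject SD, against about 4% if attempt number is modelled. These sizes rest on unrestricted orders, a linear order effect and a continuous outcome. The documents support no claim of average bias, of an invalid test, or of a known direction for the order effect.

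**What to change.** State how the sequences are generated, and load a Latin-square allocation table into REDCap before the first subject is randomized. For 25 subjects, use the 10-sequence Williams set twice plus one of its two squares; if 30 will be randomized, use the set three times. Put the rows in random order. In the Data Collection and Analysis section, specify that methods are compared with subject and attempt number in the model.

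The cost is one allocation table and one model term, with nothing changed for subjects. There are two downsides. Attempt number must then be in the analysis, because the balanced list analysed without it is conservative (size about 2.8% at 1 SD and 0.3% at 2 SD). Exact balance also loosens if subjects drop out or skip methods; the model term handles most of what remains.

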## SPECIFIC AIMS

This study will address the following specific aims and associated hypotheses:

- 1. Determine a neophyte SL wearers' preferred scleral lens application method.** *Hypothesis 1: There will be no statistical difference in the SL patient's preference among the five application methods (DMV inserter with an open or closed end, three fingers, o-ring, tea light candle) after the initial training visit.*
- 2. Determine factors that influence the amount of time it takes for a neophyte SL wearer to be able to successfully apply and remove their SLs.** *Hypothesis 2: Past contact lens experience, SL diameter, uncorrected visual acuity, and subject age will all influence the total time needed to complete all five application methods successfully.*

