#### Data Collection and Analysis

Data collection will be performed with Research Electronic Data Capture (REDCap). Data will be analyzed with STATA 16 (StataCorp LLC; College Station, TX). Means and standard deviations will be used to understand general data trends. ANOVA will be used when comparing application methods. Regression analysis will be used to find associations with the speed of being able to complete the application process. Paired t-tests will be used to compare questionnaire scores at the final visit to the baseline visit. If the assumptions of these tests cannot be met, suitable alternative statistical tests (e.g., Kruskal-Wallis) will be used.

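### The comparison of the five application methods names neither a subject term nor a position term; read literally, its error rates are wrong for ranks and for times

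*Combined protocol and SAP*

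**What the plan says.** Under Visit 2 (Dispense Visit), step 4, every subject attempts five application methods on one designated eye. REDCap is used to "determine the order by which subjects will apply their lenses"; the text does not say whether the list is balanced over positions. Each attempt is timed, with a limit: "The subject will be allowed up to 15 minutes to complete each method". The same step collects ranks: "Subjects will be asked to rank the ease of application for each method from easiest to most challenging". It anticipates tiredness twice. Subjects who reach the limit move on ("they will be instructed to do the next method to help avoid fatigue"), and "subjects will be allowed to come back on a subsequent day if they get tired".

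Hypothesis 1, under Specific Aims, states no difference in "preference among the five application methods".

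Data Collection and Analysis says "ANOVA will be used when comparing application methods", and that if assumptions fail, "suitable alternative statistical tests (e.g., Kruskal-Wallis) will be used". The type of ANOVA is not given. Pairing is specified for the questionnaire scores but not for the method comparison. No section says which test is used for the ease ranks. The sample size of 25 (30 recruited, to allow for screen failures) is stated to rest on no calculation.

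**The concern.** The five times and the five ranks from one subject are not independent. A test that treats them as 125 observations from five separate groups uses the wrong error term. For ranks, every subject has the same total, so the usual between-subject noise is absent and the test rejects too often. For times, differences between subjects go into the error term, so the test rejects too rarely and loses most of its power.

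The subjects are new to scleral lenses, so practice may help later attempts and fatigue may hurt them. Random order keeps this from favouring any method on average, but the shift still adds noise unless position is in the model.

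At stake are the ease ranks, which are the recorded data closest to Hypothesis 1, and the per-method application times. Total time (Hypothesis 2) is not affected.

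**Working it through.** The plan gives no power figure to reproduce.

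**Inputs.** From the documents: n = 25 subjects, k = 5 methods, five positions. Assumed, because the documents give none: two-sided 5% level; within-subject residual SD = 1 as the unit; within-subject correlation 0 to 0.7; one method worse by 0.6 SD; a linear shift of d SD in total from the first to the fifth attempt.

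**1. Ease ranks, no true difference.** These results need no assumed SD, correlation or trend, only complete ranks and the 5% level.
- Let B be the between-method sum of squares of the ranks. The total sum of squares is fixed at 25 × 10 = 250.
- Friedman = n(k−1) × B/250 = 100 × B/250. Tie-corrected Kruskal-Wallis = (nk−1) × B/250 = 124 × B/250, which is 1.24 times Friedman.
- Kruskal-Wallis rejects above 9.488 (chi-square, 4 df), that is, when Friedman exceeds 9.488/1.24 = 7.65. The chi-square probability is 10.5% (simulated 10.2%).
- One-way ANOVA rejects when (B/4)/((250−B)/120) > 2.447, so B > 18.86 and Friedman > 0.4 × 18.86 = 7.54. The probability is 11.0% (simulated 10.7% to 10.8%).
- Friedman at its own cutoff: 4.7%, simulated.

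**2. Times, with and without subject, no trend.**
- With subject: noncentrality = 25 × 0.6² × (1 − 1/5) = 7.2. F with 4 and 96 df gives 53% power.
- One-way: at correlation 0.5 the subject variance equals the residual variance, so the error mean square is about 1 + 1 = 2. Under the null the method mean square still has expectation 1. F is therefore roughly halved, and simulation gives type I error 0.2% and power 12%.
- Range: at correlation 0.3, type I error is about 1% and power 30%; at 0.7, type I error is near 0 and power 1% to 3%; at 0, type I error is about 5%.

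**3. Times, adding position once subject is in the model.**
- The variance of 0, d/4, d/2, 3d/4, d (divisor 4) is 0.15625d². Without position the residual variance is 1 + 0.15625d²; at d = 1.2 it is 1.225.
- Adding position changes error df from 96 to 92 (t from 1.9850 to 1.9861). Under unconstrained random orders it also multiplies the contrast variance by 1.043 on average, because method and position are not orthogonal.
- Interval width at d = 1.2, without relative to with position: √1.225 × 1.9850/1.9861 = 1.106 if orders are position-balanced; √(1.225/1.043) × 1.9850/1.9861 = 1.083 if unconstrained.
- Break-even: d = √(((1.9861/1.9850)² × q − 1)/0.15625). With q = 1 this is 0.08 SD; with q = 1.043 it is 0.53 SD.
- Power check, unconstrained, d = 1.2: noncentrality 7.2/1.225 = 5.88 gives 44% without position; 7.2/1.043 = 6.90 gives 51% with it.

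| Total shift d (SD) | Width ratio, balanced | Width ratio, unconstrained | Power without vs with, unconstrained | Power without vs with, balanced |
|---|---|---|---|---|
| 0 | 1.00 | 0.98 | 53% vs 51% | 53% vs 53% |
| 0.8 | 1.05 | 1.03 | 49% vs 51% | 46% vs 52% |
| 1.2 | 1.11 | 1.08 | 44% vs 51% | 39% vs 52% |
| 2.0 | 1.27 | 1.25 | 33% vs 51% | 22% vs 53% |

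Width ratios are from the formula and table powers from simulation. With balanced orders and no position term, type I error falls to 2.0% at d = 1.2.

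**4. Position without subject gains little.** In a one-way model with unconstrained orders, power without vs with position is 12% vs 10% at correlation 0.5. At correlation 0.3 it is 27% vs 27% for d = 1.2 and 24% vs 27% for d = 2.0.

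**The case against.** The strongest reply is that ANOVA is unspecified. A repeated-measures ANOVA is an ANOVA, and Kruskal-Wallis is only an example of a suitable alternative. That stands in part: the documents do not commit to an independent-groups analysis, and a reader who infers that they do goes beyond the text. But the only fallback named is an independent-groups test, and pairing is written out for the questionnaires and not here. The silence therefore needs filling.

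Second, Hypothesis 1 concerns preference, the recorded ranks concern ease, and no test is assigned to them. This stands. The 10.5% to 11% figures hold only if the named tests are applied to those ranks.

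Third, the study is preliminary, has no power target, and gives no data on trend. This stands for position: its benefit is conditional, and at no trend it costs a little. It does not excuse the missing subject term, whose effect on the ranks needs no assumed trend or SD.

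Two stronger readings are tempting. A reader might infer that practice or fatigue biases the comparison; random order rules out systematic bias, so only precision is affected. A reader might also take 1.2 SD as the point below which position is not worth including; it is only about where the gain in interval width reaches 10%, and break-even is far lower.

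**Conclusion.** The concern holds, mainly because of subject. Taken literally, the named tests roughly double the false-positive rate on complete ease ranks (10.5% to 11% instead of 5%). For times they make the comparison very conservative: type I error under 1% and power of about 12% instead of 53%, at an assumed correlation of 0.5 and an assumed 0.6 SD difference.

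Position is a secondary matter of precision. With subject in the model and a linear shift, adding it pays from about 0.1 SD (balanced orders) to 0.5 SD (unconstrained orders) over the five attempts. At 1.2 SD, omitting it costs 8% to 11% in interval width, or about 7 points of power under unconstrained orders. SD here means within-subject residual SD. The documents give no trend, SD or correlation, so the size of the position gain is not known. The plan should be changed before the data are analysed.

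**What to change.** In Data Collection and Analysis:

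1. Compare application times with a model that has method and position (1 to 5, categorical) as fixed effects and subject as a blocking or random effect. Include both terms together.
2. Name Friedman, or an equivalent within-subject rank test, for the ease ranks, and replace Kruskal-Wallis with it as the non-parametric fallback for the method comparison. A position-adjusted rank test is optional.
3. Report the estimated position effect.

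Cost: 4 degrees of freedom plus slight non-orthogonality under unconstrained orders, together about 2 points of power if there is no trend (53% to 51%), and about none if orders are position-balanced. No subjects, visits or procedures are added.

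Limits: the position term does not deal with carryover that differs between methods, attempts split over days, or capped and stopped attempts. Removal times should not serve as a device-free check on practice or fatigue unless the report states that removals are observed only after successful applications.

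### The Hypothesis 2 outcome has no value for a subject who abandons or times out on any method, and the planned regression has no rule for that subject

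*Combined protocol and SAP*

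**What the plan says.** The outcome is set in Specific Aims. Hypothesis 2 states that past contact lens experience, lens diameter, uncorrected acuity and age "will all influence the total time needed to complete all five application methods successfully". Success with every method is part of the definition.

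The conduct is set in Visit 2: Dispense Visit, step 4 (Randomization). "Subjects will be timed during each application", and there are two ways past a method without success:

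- Giving up: "If a subject is unsuccessful with a method and declines to continue that method after being encouraged, the time will be recorded". The stop is also logged: "If a patient stops a procedure before completing an application, this event will be recorded".
- Running out of time: "The subject will be allowed up to 15 minutes to complete each method", and "If the subject is unable to complete the method within that time frame, they will be instructed to do the next method".

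The analysis is set in Data Collection and Analysis: "Regression analysis will be used to find associations with the speed of being able to complete the application process". If test assumptions fail, "suitable alternative statistical tests (e.g., Kruskal-Wallis) will be used". Neither sentence says how an unsuccessful attempt enters the analysis.

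**The concern.** The protocol expects some attempts to fail, yet one failure in five leaves the subject without a value for the Hypothesis 2 outcome. The analyst must then improvise. A regression on the outcome as worded loses the subject. A regression on the sum of recorded times keeps the subject but reads a stop or time-out as a completion, so someone who gives up early looks fast.

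Hypothesis 2 asks which factors make training slow, and the gap concerns the slowest subjects. With 25 subjects and four covariates there is little room to lose any. Without a stated rule, the choice can also be made after the data are seen.

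**Working it through.** **No plan figure to reproduce.** Study Design gives no power, effect size, application time or failure rate. Its only arithmetic, 25 + 5 = 30, is correct. From the documents I take n = 25, five methods, a 15-minute limit and four covariates. Everything else below is assumed.

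**Step 1: how many subjects have a defined outcome.** If p is the success probability per method and failures are independent, the expected number is 25 × p^5.

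- p = 0.95: 25 × 0.774 = 19.3
- p = 0.90: 25 × 0.590 = 14.8
- p = 0.80: 25 × 0.328 = 8.2

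If failures cluster within subjects (beta-binomial, intraclass correlation 0.5), the probabilities of five successes are 0.890, 0.790 and 0.613, giving 22.3, 19.7 and 15.3 subjects. At 95% success per method, about 19 to 22 of 25 therefore have an outcome.

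**Step 2: what each handling does to the slope.** Simulation of 400,000 subjects with five attempts each:

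- Time to success is log-normal, with a covariate effect of 0.25 log units per SD, subject SD 0.35 and residual SD 0.6.
- Stop time is log-normal with SD 0.5. A median of 100 minutes means almost nobody stops before the limit. A median of 10 minutes, lowered by 0.4 log units per covariate SD, means frequent stopping that depends on the covariate.
- An attempt succeeds if the time to success comes before both the stop time and 15 minutes.
- The reference is the slope of the uncapped total time to success, in minutes per covariate SD.
- Bias = slope under the handling ÷ reference − 1.

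| Median time per method | Stopping | Reference | Drop subject | Sum recorded times |
|---|---|---|---|---|
| 4 min | almost none (96% success) | 6.55 | 3.91 (about −40%) | 5.60 (about −15%) |
| 2 min | almost none | 3.27 | 2.91 (about −11%) | 3.19 (about −2%) |
| 1 min | almost none | 1.64 | 1.62 (about −1%) | 1.64 (under 1%) |
| 4 min | frequent, covariate-dependent (80% success) | 6.55 | 1.23 (about −81%) | 1.68 (about −74%) |

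For the first row: 3.91 ÷ 6.55 − 1 = −0.40 and 5.60 ÷ 6.55 − 1 = −0.15. For the last: 1.23 ÷ 6.55 − 1 = −0.81 and 1.68 ÷ 6.55 − 1 = −0.74.

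**Step 3: scoring every failure at 15 minutes.** With almost no early stopping this equals summing, so it is also about −15% at a 4-minute median. In the last row it gives 10.36 ÷ 6.55 − 1 = +58%. The error can go either way, so this rule is not a safe default.

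**Step 4: does the fallback help?** No. It is triggered by failed test assumptions, and a rank test such as Kruskal-Wallis still needs a value for each failed attempt.

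**The case against.** **The data are not lost.** This is true. Stop times and stop events are recorded and a time-out is known to be 15 minutes. A reader might infer that the plan discards subjects who fail. The documents do not say so; they name no rule at all. What is missing is an analysis rule, not data.

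**The effect may be negligible.** This stands in part. The documents give no application times, and if most subjects succeed within a minute or two and few stop early, the bias is small (second and third rows of the table). A reader might infer that Hypothesis 2 is necessarily badly biased, and the documents do not support that either. But they do not support assuming rare failures: step 4 makes specific provision for them.

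**The study is preliminary, and a censored mixed model is more than it needs.** The preliminary status is stated, and a long model specification would be out of proportion. The core of the repair is a short rule. It needs a censored outcome because no single number entered for a failed attempt represents a time to success.

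**A simulation can flatter the recommended model.** Agreed. Data generated as log-normal and analysed as log-normal will return the true effect by construction, and a power comparison that also changes the outcome scale does not isolate the handling of failures. I use neither as support. The case for censoring is that it uses what is recorded, namely that success had not occurred by a known time.

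**Conclusion.** The gap is real and should be fixed. Hypothesis 2 requires success with all five methods, step 4 lets subjects proceed without it, and the analysis section does not connect the two. In the scenarios run, both literal readings pull the association toward zero when failures occur, from about 1% or less to about 80% depending on the assumed speed and stopping. That range rests wholly on assumed inputs and on one effect size. It shows that the unstated rule can matter, and does not predict what this trial will find. The direction for summing also assumes that slower subjects do not persist longer before giving up.

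A reader might extend the point to Hypothesis 1. That hypothesis concerns preference, which subjects rank after trying the methods, and it is not directly affected.

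Aim 2 also covers removal. Step 4 asks for removal only from subjects who managed to apply the lens, so removal times are absent after a failed application and need the same attention.

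**What to change.** In Data Collection and Analysis, with Hypothesis 2 reworded to match:

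1. Analyse time to successful application per method. Right-censor abandoned attempts at the recorded stop time and time-outs at 15 minutes. Use a censored or time-to-event regression with a term for method, the four named covariates and a subject-level random effect, or another allowance for five attempts per subject.
2. Report the number of successes per method and the number of subjects who succeeded with all five.
3. Add one sensitivity analysis that scores failures as worst rank.
4. Apply the same rule to any analysis of removal time.
5. State that the main analysis assumes stopping is non-informative given the covariates.

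The cost is wording only: no new data, visits or procedures, and no change to how subjects are trained. The downside is a somewhat more complex model that depends on the assumption in item 5 and still rests on about 25 subjects.
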